3.2. Planned Number of Patients and Countries

A total of 388 patients will be enrolled in the study (accounting for 10% early dropouts) and the total number of evaluable patients is planned to be 350 (200 patients in the DS group and 150 patients in the SoC group). Details on definition of evaluable patients and sample size are given in Section 9.1.

The study is planned to be conducted in the US in approximately 45 investigational centers. The study is expected to start in Q1 2021 and last until approximately Q2 2022.

3.3. Justification for Study Design and Selection of Population

Sample size estimates are based upon the assumption that the absolute differences between the DS and SoC groups and the associated operational characteristics will be similar to the absolute differences and operational characteristics of the DS and SoC groups noted in the sample size rationale for the study design.

The population for the study was chosen based on level of asthma control, as the objective of the study is to assess potential improvement in asthma control with the FS eMDPI DS and Albuterol eMDPI DS.

3.4. Stopping Rules for the Study

There are no formal rules for early termination of this study. During the conduct of the study, serious adverse events will be reviewed (Section 7.1.5) as they are reported from the investigational centers to identify safety concerns.

The study may be terminated by the sponsor for any reason at any time. For example, the sponsor should terminate the study in the event of the following:

- new toxicological or pharmacological findings or safety issues invalidate the earlier positive benefit-risk assessment
- discontinuation of the development of the IMP or device

If the whole study is stopped, patients who are terminated early will be followed according to Withdrawal Criteria and Procedures for the Patient (Section 4.3).

3.5. Schedule of Study Procedures and Assessments

Study procedures and assessments with their time points are presented in Table 5. Detailed descriptions of each method of procedures and assessments are provided in Section 6 (efficacy assessments) and Section 7 (safety assessments). Study procedures and assessments by visit are listed in Appendix B.

Table 5: Study Procedures and Assessments

Study period	Screening/ Baseline visit	Treatment period (24 weeks)					Follow- up telephone call ^a	Clinically driven assessment(s) (if necessary)			
									End of treatment/ ET visit		
Visit number	Visit 1	DTP	DTP	DTP	Visit 2 ^b		DTP	DTP	Visit 3		
Treatment week		W3	W6	W9	W12	W15	W18	W21	W24	W26	
Day and allowed time windows	Day 1 ^c				84 days ±3 days				168 days +3 days	182 +7 days	
Procedures and assessments											
Informed consent/assent	X										
Inclusion and exclusion criteria	X										
Medical history	X										
Current medication and treatment history related to asthma	X										
Inform patients of study restrictions and compliance requirements	X										
ACT ^d	X				Xe				X		
Mini-AQLQ and WPAI ^d	X								X		
BMQ-S11 and BIPQ ^d	X								X		
Assign patient number and provide unique email account for DS group patients	X										
Train DS group in use of test IMP	X										
Dispense test IMP to DS group											
FS eMDPI ^f	X	X	X	X	X	X	X	X			X
Albuterol eMDPI ^g	X				X						
Dose confirmation of test IMP in IRT ^h	X	X	X	X	X	X	X	X			X ⁱ
Registration and onboarding (App)	X										

Version 2.0

CLN0035849

Page 41 of 98

Approved

Study period	Screening/ Baseline visit	Treatment period (24 weeks)						Follow- up telephone call ^a	Clinically driven assessment(s) (if necessary)		
									End of treatment/ ET visit		
Visit number	Visit 1	DTP	DTP	DTP	Visit 2 ^b	DTP	DTP	DTP	Visit 3		
Treatment week		W3	W6	W9	W12	W15	W18	W21	W24	W26	
Day and allowed time windows	Day 1 ^c				84 days ±3 days				168 days +3 days	182 +7 days	
Procedures and assessments											
Adverse events and adverse device effects inquiry	X				X				X	X	X
iHCP will ask Asthma Management questions regarding adherence, inhaler technique, treatment adjustments, and biologic medication usage					X				X		X
Vital signs measurement	X								X		
Concomitant medication inquiry	X				X				X		X
Administer post- intervention PRO (SUS) to DS group patients ^j									X		
Administer SUS to iHCPs									X		
Test IMP collection and accountability					X				X		
Remove App from the patient's smart device (DS group)									X		
Confirmation that patient has returned to previous asthma treatment (DS group)		2.11			II Con the a l					X	

^a End of study is defined as the follow-up telephone call for the last patient.

CLN0035849 Version 2.0 Approved Page 42 of 98

b This visit may be in-person or remote.
c Screening and enrollment are expected to occur on the same day. The maximum allowable duration between screening and enrollment is 7 days.

Clinical Study Protocol with Amendment 01

- d The ACT is to be completed first by all patients, followed by the Mini-AQLQ, WPAI questionnaire, BMQ, and then the BIPQ, all to be completed by patients 18 years of age or older, and should precede any discussion between the patient and investigational center personnel.
- ^e If necessary, this questionnaire may be administered by telephone for this visit.
- f At Visit 1, patients will be provided the test IMP, along with training on use and proper technique, by the investigational centers. New FS eMDPI devices will be shipped directly to the patient periodically after Visits 1 and 2. Upon receipt, the patient will pair the new device with the App. The patient will immediately stop using the old device and switch to the new device. If Visit 2 is in-person at the investigational center, a new FS eMDPI device will be dispensed at that visit.
- ^g Patients will receive an Albuterol eMDPI device, along with training on use and proper technique, at Visit 1 [Day 1] and Visit 2 [Week 12]). Extra Albuterol eMDPI devices may be shipped as needed, based on the clinical judgment of the investigator. Upon receipt, the patient will pair the new device with the App. The patient will immediately stop using the old device and switch to the new device.
- h To trigger DTP shipments, after Visit 1, the investigational center will receive periodic email reminders to access the IRT system to confirm the dose of test IMP to be shipped to the patient. Confirmation must occur within ±2 days of the email date and is required before the next shipment can be sent. The investigational center will be asked to confirm the dose of FS eMDPI and to specify whether an Albuterol eMDPI should be included in the next shipment (if not already scheduled). The 3-day visit windows do not apply to dose confirmation. Email reminders will be triggered based on the date of the previous visit or DTP shipment. If there is a need to send an additional DTP shipment outside of the regularly scheduled shipments (eg, for an additional or replacement device), it will be done in addition to the scheduled shipments.
- ⁱ Dose confirmation at a Clinically Driven Assessment visit should be performed only if the patient's dose is being changed at this visit.
- ^j The SUS should be the last questionnaire provided to patients, 18 years of age or older, at the end of treatment visit or at the ET visit. Each investigational center will receive 1 SUS questionnaire, regarding the use of the dashboard, to complete following the last patient visit at the investigational center.

ACT=Asthma Control Test; App=smart device application; BIPQ=Brief Illness Perception Questionnaire; BMQ-S11=Beliefs about Medicines Questionnaire-Specific; DS=Digital System; DTP=direct-to-patient; eMDPI=multidose dry powder inhaler with integrated electronic module; ET=early termination; FS=fluticasone propionate/salmeterol; iHCP=investigational center health care provider; IMP=investigational medicinal product; IRT=interactive response technology; Mini-AQLQ=Mini Asthma Quality of Life Questionnaire; PRO=patient-reported outcome; SUS=System Usability Scale; W=week; WPAI=Work Productivity and Activity Impairment.

CLN0035849 Version 2.0 Approved Page 43 of 98

4. SELECTION AND WITHDRAWAL OF PATIENTS

Prospective waivers (exceptions) from study inclusion and exclusion criteria to allow patients to be enrolled are not granted by Teva (Appendix C). Changes to inclusion or exclusion criteria are indicated below and detailed in Section 16.

4.1. Patient Inclusion Criteria

Patients may be randomized/enrolled in this study only if they meet all of the following criteria:

- a. The patient is 13 years or older at the time of screening.
- b. The patient has a documented diagnosis of asthma established at the investigational center at the time of informed consent or the investigator confirms a diagnosis of asthma.
- c. The patient is currently on treatment with a moderate- to high-dose ICS with LABA.
- d. The patient has an ACT score of less than 19 at the screening or baseline visit.
- e. The patient is willing to discontinue all other maintenance ICS with LABA medications and rescue medications and replace them with the study-provided FS eMDPI and Albuterol eMDPI, respectively, for the duration of the trial, if randomized to the DS group. All other asthma maintenance medications, except for ICS with LABA, may be continued.
- f. The patient can read and communicate in English and is familiar with and is willing to use his/her own smart device that meets the minimum App requirements and download and use the App.
- g. The patient is able to provide written informed consent.
- h. The patient must be willing and able to comply with study requirements and restrictions and to remain at the investigational center for the required duration during the study period, and willing to return to the investigational center for the follow-up procedures and assessments as specified in this protocol.

4.2. Patient Exclusion Criteria

Patients will not be randomized/enrolled in this study if they meet any of the following criteria:

- a. [Revision 1] The patient has previously participated in a Digihaler study or is currently being treated prior to enrollment with a digital inhaler system, including the Digihaler system or an external "bolt on" digital system designed to monitor inhaler usage, such as the Propeller Health or Adherium systems.
- b. The patient has any clinically significant uncontrolled medical condition (treated or untreated) other than asthma, which in the view of the investigator would preclude participation.

44

c. The patient was hospitalized for severe asthma in the last 30 days.

Version 2.0

CLN0035849

- d. The patient has any medical or psychiatric condition that, in the opinion of the investigator, could jeopardize or would compromise the patient's ability to participate in this study.
- e. The patient has a diagnosis of chronic obstructive pulmonary disease (COPD) or asthma-COPD overlap (ACO).
- f. The patient is a current smoker or has a greater than 10 pack-year history of smoking.
- g. The patient is currently being treated with systemic corticosteroids (oral, intramuscular, or intravenous) or has been treated within the last 30 days.
- h. The patient has any treatment with biologics for asthma (eg, omalizumab, anti-interleukin (IL)5, anti-IL5R, anti-IL4R), or has had such treatment within the last 90 days. (However, during the study, patients can be escalated to therapy with such agents if clinically indicated in the judgement of the investigator as part of their asthma management and remain in the study.)
- i. The patient has a known hypersensitivity to any components of the IMPs stated in this protocol.

4.3. Withdrawal Criteria and Procedures for the Patient

Each patient is free to withdraw from the study or discontinue from IMP or using the devices at any time, without prejudice to their continued care. Patient must be withdrawn from the study if any of the following events occur:

- 1. Patient withdraws consent or requests discontinuation from the IMP or withdrawal from the study for any reason.
- 2. Patient develops an illness that would interfere with his/her continued participation.
- 3. Patient is noncompliant with the study procedures and assessments or administration of FS eMDPI or Albuterol eMDPI, in the opinion of the investigator.
- 4. Patient takes prohibited concomitant medications as defined in this protocol (ie, other SABA products).
- 5. The sponsor requests withdrawal of the patient.
- 6. Patient experiences an adverse event or other medical condition which indicates to the investigator that continued participation is not in the best interest of the patient.

Patients should be treated with SoC after withdrawal from or termination of the study as appropriate.

Investigators should attempt to obtain information on patients in the case of withdrawal from the study or discontinuation from IMP. Results of any evaluations and observations, together with a narrative describing the reason(s) for withdrawal from the study or discontinuation from IMP, must be recorded in the source documents. The case report form (CRF) must document the primary reason for withdrawal from the study or discontinuation from IMP.

See Appendix E for information regarding how the study will define and address patients who are lost to follow-up to help limit the amount and impact of missing data.

If the reason for withdrawal from the study or discontinuation from IMP is an adverse event and/or adverse device effect, monitoring will be continued as applicable (eg, until the event has resolved or stabilized, until the patient is referred to the care of a healthcare professional, or until a determination of a cause unrelated to the IMP or study procedure is made). The specific event or test result (including repeated test results, as applicable) must be recorded both on the source documentation and in the CRF; both the adverse events page and/or adverse device effect page and the termination page of the CRF will be completed at that time. The investigator must inform the contract research organization (CRO) as soon as possible of each patient who is being considered for withdrawal due to adverse events. Additional reports must be provided when requested.

If a patient is withdrawn from the study or discontinues IMP for multiple reasons that include adverse events, the relevant page of the CRF should indicate that the withdrawal was related to an adverse event. An exception to this requirement will be the occurrence of an adverse event that in the opinion of the investigator is not severe enough to warrant discontinuation but that requires the use of a prohibited medication, thereby requiring discontinuation of the patient. In such a case, the reason for discontinuation would be "need to take a prohibited medication," not the adverse event.

In the case of patients lost to follow-up, attempts to contact the patient must be made and documented in the patient's medical records and transcribed to the CRF.

All assessments should be performed according to the protocol for the end of treatment visit or upon early termination if possible. Patients are required to return the FS eMDPI and Albuterol eMDPI (used and unused) upon withdrawal from the study.

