3. STUDY DESIGN

3.1. General Study Design and Study Schematic Diagram

This is a 24-week treatment, multicenter, open-label, randomized, parallel group comparison feasibility study of SoC treatment versus using the eMDPI DS, including inhaler, App, DHP (Cloud solution), and dashboard, to optimize outcomes in patients at least 13 years of age or older with asthma.

The study will consist of a screening/baseline visit (Visit 1), a 24-week, open-label treatment period with Visit 2 (either in-person or remote) at Week 12 and Visit 3 at Week 24, and a follow-up telephone call (2 weeks following treatment completion).

Patients with suboptimal asthma control will be enrolled in the study and randomized, in a 4:3 ratio, respectively, to 1 of 2 parallel groups (Table 4), stratified by investigational center.

Table 4: Description of Treatment Groups

DS group	SoC group
FS eMDPI ^a + App	Current ICS/LABA and any additional controller medication for asthma (except for biologics)
Albuterol eMDPI + App	Current rescue medication
DHP (Cloud solution)	Not applicable
Provider-facing dashboard	Not applicable

^a iHCP can add another controller medication other than an ICS with LABA, including a biologic, to the DS patient's treatment, if needed.

Albuterol eMDPI=Albuterol electronic multidose dry powder inhaler; App=smart device application; DHP=Digital Health Platform; DS=Digital System; FS eMDPI=fluticasone propionate/salmeterol electronic multidose dry powder inhaler; ICS=inhaled corticosteroid; iHCP=investigational center health care provider; LABA=long-acting beta₂ agonist.

The DS group patients will use the FS eMDPI and the Albuterol eMDPI with a common App, DHP (Cloud solution), and dashboard. The SoC group patients, who will include eligible patients treated with their current treatment provided by the investigational center to the patient, based on asthma guidelines, will not use the DS during the treatment period. Similar data will be collected regarding outcomes for both groups: ACT after 24 weeks, BMQ, BIPQ, Mini-AQLQ, and WPAI questionnaire responses, and the frequency of CAEs.

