5.6. Prior and Concomitant Medication or Therapy

Any concomitant medication a patient is taking at screening and up to the end of treatment/ET visit will be recorded on the CRF. Trade name and international nonproprietary name (if available), indication, dose, and start and end dates of the administered medication will be recorded. The sponsor will encode all medication according to the World Health Organization (WHO) drug dictionary (WHO Drug).

The use of other SABA products, by the DS group, is prohibited during this study except for the use of nebulized albuterol, as needed, in the ED for an acute exacerbation of asthma.

CLN0035849 Version 2.0 Approved Page 53 of 98

At Visit 2 and the end of treatment visit (Visit 3), patients will be asked whether they have taken any medications (other than IMPs), including over-the-counter medications, vitamins, or herbal or nutritional supplements, since the previous visit.

Concomitant medication and treatment will be recorded through the final visit.

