5.7. Procedures for Monitoring Patient Compliance

The investigator will be responsible for dispensing IMPs, training patients on the correct use of IMPs, return of IMPs, and IMP accountability records will be completed.

If the investigator or the sponsor determines that the patient is not in compliance with the study protocol, the investigator and the sponsor should determine whether the patient should be withdrawn from the study.

Exposure to IMP will be assessed as required. Since the Albuterol eMDPI (IMP) is a rescue medication, it will be used on an "as needed" basis.

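### Protocol 4.3 compels study withdrawal for two events that only DS patients can have, so the Week 24 ACT of those patients is replaced or lost; Protocol 5.7 and Appendix C leave the same decision open

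*Protocol*

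**What the plan says.** Protocol 4.3 introduces a numbered list of events with compulsory language: a patient who meets any of them has to leave the study. Item 3 reads "Patient is noncompliant with the study procedures and assessments or administration of FS eMDPI or Albuterol eMDPI, in the opinion of the investigator". Item 4 reads "Patient takes prohibited concomitant medications as defined in this protocol (ie, other SABA products"). Later in the section, an adverse event that would not itself justify stopping still leads to exit if it "requires the use of a prohibited medication, thereby requiring discontinuation of the patient", and the recorded reason is then the medication, not the event.

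Protocol 5.6 limits the ban to one arm: "The use of other SABA products, by the DS group, is prohibited during this study", with an exception for nebulized albuterol in the emergency department. Table 4 in Protocol 3.1 gives the standard-of-care (SoC) arm "Current rescue medication".

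Two other places are not compulsory. Under Protocol 5.7, when a patient is found noncompliant, "the investigator and the sponsor should determine whether the patient should be withdrawn from the study". Appendix C names IMP noncompliance and prohibited-medication use among possible important deviations, and lets the sponsor, with medical-expert approval, keep such a patient in the study.

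On scoring, SAP 6.2.2 says data collection ends when treatment is discontinued. Neither noncompliance nor prohibited medication is on the nonresponder lists in SAP 4.3 or 6.2.2, so the ET value is used. SAP 4.3 counts an early exit with no ET visit as a failure. SAP 3.1.2 requires a post-baseline ACT for mITT. On the ET visit itself, Protocol 4.3 says "All assessments should be performed according to the protocol for the end of treatment visit or upon early termination if possible".

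**The concern.** The trial is open-label and tests a system meant to change how patients use their inhalers. Poor inhaler use and a return to an old reliever are therefore part of what happens under the DS strategy. If either leads to compulsory removal, the primary outcome at Week 24 goes unobserved for some DS patients, under a rule with no SoC counterpart. Weekly dashboard review makes eMDPI noncompliance easier to see in DS. It does not make other-SABA use easier to see, because Protocol 5.1.2.3 limits the dashboard to inhaler-use data and App self-assessments.

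At stake is the like-for-like comparison of Week 24 response. Consistency is a second issue: across about 45 centers, one may follow the compulsory wording of 4.3 and another the discretion in 5.7 or Appendix C for the same event. Withdrawal reasons are tabulated by arm (SAP 5.1 and 5.2), so the number of such exits will be known at the end. The missing Week 24 ACT will not.

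**Working it through.** **Who can meet each trigger**

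| Event | DS | SoC |
|---|---|---|
| Item 3, study procedures and assessments | yes | yes |
| Item 3, eMDPI administration | yes | no (no eMDPI) |
| Item 4, other SABA | yes, except nebulized albuterol in the ED | no (ban is DS-only) |
| Discretionary exit (item 5, 5.7, Appendix C) | yes | yes |

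**What happens to the outcome**

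1. ET visit done: the ET ACT stands in for Week 24.
2. No ET visit, but a Visit 2 ACT exists: failure.
3. No post-baseline ACT: outside mITT.

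Sensitivity analysis 1 (SAP 6.2.3) multiply imputes patients without an ET visit, so it examines route 2. It keeps ET values, so route 1 is unchanged. Sensitivity analysis 2 only removes the center effect.

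**The plan's own figure**

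Inputs from Protocol 9.1 and SAP 2.4: response 58% DS and 45% SoC, 200 and 150 patients, priors Beta(0.5, 0.5) for DS and Beta(9.52, 11.88) for SoC, success if the posterior probability that OR > 1 is at least 0.95. Exact enumeration over both binomials, without covariate or center, gives 81.7%; the plan says about 82%.

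Dropouts kept in the analysis as ET values or failures make the randomized total the better base: 388 × 4/7 ≈ 222 and 388 × 3/7 ≈ 166. The same rule then gives 84.9%. With 45% in both arms, the probability of success is 4.6% at 200/150 and 4.7% at 222/166.

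**Illustration of routes 1 and 2**

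The documents supply none of these four quantities; all are assumptions:

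- k = share of DS leaving this way
- w = their Week 24 response had they stayed
- d = ET response minus Week 24 response
- f = share with no ET visit, scored as failures

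DS rate = 0.58 − k·w + k·(1 − f)·(w + d)

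With k = 0.05 (about 11 of 222):

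| Scenario | DS rate | Success, 200/150 | Success, 222/166 |
|---|---|---|---|
| f = 0, d = 0 | 0.580 | 81.7% | 84.9% |
| f = 0, d = −0.10 | 0.575 | 78.9% | 82.3% |
| f = 0, d = −0.20 | 0.570 | 75.9% | 79.4% |
| f = 0, d = +0.10 | 0.585 | 84.2% | 87.2% |
| f = 0, d = +0.20 | 0.590 | 86.6% | 89.3% |
| f = 0.25, d = 0, w = 0.30 | 0.57625 | 79.6% | 83.0% |
| f = 0.50, d = 0, w = 0.58 | 0.5655 | 73.0% | 76.6% |
| f = 1, w = 0.30 | 0.565 | 72.7% | 76.3% |
| f = 1, w = 0.58 | 0.551 | 62.6% | 66.4% |

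For example, the last row is 0.58 − 0.05 × 0.58 = 0.551. Over the same scenarios the shift in DS rate runs from −1.45 to +0.5 points at k = 0.025 and from −5.8 to +2.0 points at k = 0.10.

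**Illustration of route 3**

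Assume no true effect (45% in both arms), 5% of 200 DS patients lost from mITT (190 left), and a would-be response q among those lost. The remaining DS rate is (0.45 − 0.05·q)/0.95. With q = 0 it is 0.474 and false success is 11.3%; with q = 0.30 it is 0.458 and 6.4%. The reference is 4.6%. This route can therefore favor DS, while failure scoring works against it.

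**The case against.** The other side has several good points.

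- Item 3 rests on the investigator's opinion, and 5.7 makes it a joint decision with the sponsor. The rest of the protocol manages poor inhaler use with the patient still in the study: weekly review, adherence discussions, and adherence as secondary endpoint #3. Few patients may be removed. This stands, and it limits the likely size. It also shows that the wording of 4.3 does not match the intent.
- Item 4 is narrowed by the emergency-department exception, and extra albuterol devices can be shipped. This stands.
- Every early exit already has a scoring rule, and Sensitivity analysis 1 tests failure scoring. This stands in part: a rule exists, but no rule or imputation yields the Week 24 ACT.
- Using Week 24 ACT whatever the adherence is a different estimand strategy. True, but the plan gives no reason for ending follow-up in one arm on these grounds, and the visit is already scheduled.
- Sponsor involvement in 5.7 and Appendix C limits divergence between centers. This stands in part; 4.3 itself does not send centers to that route.

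A reader might infer more: that 4.3 biases the trial against DS (or for it), that every poor adherer is removed automatically, or that secondary endpoint #2 is already miscounted. The documents do not support these readings. Direction depends on which scoring route applies, item 3 involves judgment, and the endpoint #2 problem arises mainly if other-SABA users are retained, as the fix proposes.

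**Conclusion.** The concern holds as a design and wording flaw. Two compulsory withdrawal triggers can be met only by DS patients, they conflict with 5.7 and Appendix C, and each such exit replaces or removes a Week 24 primary outcome that the schedule would otherwise collect.

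Its size cannot be derived from the documents. If 5% of DS left this way, the success probability at 222/166 would be 66% to 89%, against 85%. The low end needs every such patient to have no ET visit and to have been as likely to respond as the rest of the arm. The high end needs ET response 20 points above Week 24 response. If the two responses are equal and all attend an ET visit, nothing moves. These figures show sensitivity and are not a forecast. Because frequency and direction are both unknown, observing the outcome is safer than relying on a replacement rule. This is a change the team should make; it does not invalidate the primary analysis.

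**What to change.** 1. Protocol 4.3: remove item 4 and the eMDPI-administration half of item 3 from the events that compel study withdrawal. Record them as adherence data or protocol deviations, keep the patients on the Visit 2 and Visit 3 schedule, and collect the Week 24 ACT. Safety exits remain under item 6, and other SABAs stay prohibited for DS under 5.6.
2. Bring the later text in 4.3 on adverse events needing a prohibited medication, Protocol 5.7 and Appendix C to the same rule.
3. SAP 4.3 and 6.2.2: use the observed Week 24 ACT for retained patients. State that the nonresponder rule for disliking the DS or the IMP still applies to anyone who discontinues treatment for that reason, so that patients who stop for the same reason are scored alike.
4. SAP 6.3.2, as a consequence of change 1: a week with no recorded inhalations is currently scored as zero SABA use and 7 SABA-free days, which would be wrong for a retained patient using another SABA. Flag patients with recorded other-SABA use and report endpoint #2 with and without their recorded periods of use. Concomitant-medication records help only partly: "dose, and start and end dates of the administered medication will be recorded", but such dates do not reliably identify the weeks in which an as-needed drug was taken.

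Cost: wording in three places of the protocol and three of the SAP, with no new visit or assessment. The downsides are follow-up of a few more patients, slightly lower reported adherence, and some flagged endpoint #2 data.
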